6.1.2 Efficacy Analysis

Key contrasts will compare the level of each endpoint before and after treatment by comparing the differences of model-based expected values at the end of treatment and expected values at baseline. These expected values will arise out of the implementation of mixed effects models that will adjust for any relevant changes in patient characteristics over time (such as changes in growth and pubertal status) as well as for any baseline factors that predict dropout. Alternative contrasts will compare the trajectories (slopes) of endpoints over time prior to the intervention against the slopes after the start of treatment.

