Study Treatment: A single blinded randomized trial of levothyroxine treatment (starting dose 0.5 – 1 mcg/kg daily) using a switching replication design. Subjects will be randomized into 2 groups of 10.

(Group 1) Delayed treatment group: 6 months of placebo followed by 6 months of levothyroxine treatment

(Group 2) Immediate treatment group: 12 months of levothyroxine treatment

Follow-Up: Studies will be obtained at baseline, 6 months, 12 months, and 18 months. Interim thyroid studies will be checked at 3 months, 6 weeks after randomization (month 7.5); month 13.5 and 6 weeks after any dose adjustment.

Efficacy Evaluations

TSH

T4

Anthropometry (HT-Z, WT-Z, BMI-Z),

body composition by DXA,

PWV & PWA

Blood lipid panel, non-HDL-C, lipoprotein subclass analysis, glucose, plasma insulin, HOMA-IR, hs-CRP, IL-6, PAI-1, adiponectin, leptin,

QOL, Body Image, physical activity assessment.

Safety Evaluations

To monitor for safety, data will be made available to investigators every 3 months. The PI will not be blinded to the treatment arm, will be making dose adjustments, and for safety purposes, TSH and T4 data will be available to the PI as soon as it is available.

Interview at 4 and 6 weeks after treatment initiation and at each visit to document intensity and frequency of any AE.

Any AEs and SAEs will be reported to the CTRC and the IRB within the allotted time frame.

Statistical And Analytic Plan

Standard mixed effects piecewise longitudinal data model ⁽²⁾ will be used to estimate in a single model both longitudinal (within subject) and cross-sectional (across subject) effects of the intervention. Cross-sectional comparisons will be possible for the second 6-month period of observation when ½ of subjects will be switched to treatment while the other ½ will take a placebo.

DATA AND SAFETY MONITORING PLAN

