3.1.3 Treatment Phase

Randomization and blinding -

Only subjects with persistently elevated TSH (5 – 10 mIU/mL) will be randomized into the following 2 groups of 10: Group 1 (Delayed treatment) or Group 2 (Immediate treatment). A 3 month supply of placebo will be dispensed to subjects that have been randomized into Group 1 and a 3-month supply of levothyroxine will be dispensed to subjects randomized into Group 2.

Blood Draw Visit B (7.5 Month): TSH and T4 will be measured 6 weeks after the Study Visit #2 (approximately 7.5 months from the start of the study). Subjects will obtain a blood draw. Dose adjustments will be made for Group 2 as needed. Another 3-month supply of placebo or levothyroxine (dose adjusted as necessary) will be mailed to the home. Subjects requiring dose adjustments will have TSH and T4 in another 6 weeks to confirm/assure TSH is in the desired range.

Study Visit #3 (12 Month): – Subjects and their parents/guardians will present to the research facility following a 12-hour overnight fast. At this study visit, the subject will have the following measures: fasting blood samples, TSH, T4, anthropometric measurements, whole body DXA scan, blood pressure, pubertal assessment and questionnaire assessments. Females will receive a urine pregnancy test. Females found to be pregnant will be disqualified from the study and will receive appropriate counseling and referral. After the study visit, subjects will be asked to wear a physical activity arm band at home for 7 days, and a 3 day dietary recall will be done by telephone. TSH and T4 will be reviewed and levothyroxine will now be dispensed to both Groups 1 and 2. Group 2 will continue on current dose if TSH within range; otherwise dose adjustments will be made as necessary.

Blood Draw Visit C (13.5 Month): TSH and T4 will be measured 6 weeks after the 12 month visit (approximately 13.5 months from the start of the study). Subjects will have blood drawn. A subsequent blood draw 6 weeks later will be required for any dose adjustments.

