6 STATISTICAL CONSIDERATIONS

6.1 Statistical Methods

6.1.1 Baseline Data

Data management will proceed as with Aim 1, with particular attention to obtaining all information on each subject at each encounter. Subject retention in our previous studies of children with DS has been excellent.

Estimates will be based on a standard mixed effects piecewise longitudinal data model⁽²⁾, implemented in the Stata v 12 program “xtmixed”, to estimate in a single model both longitudinal (within subject) and cross-sectional (across subject) effects of the intervention. Cross-sectional comparisons will be possible for the second 6-month period of observation when ½ of subjects will be switched to treatment while the other ½ will take a placebo. A piecewise model allows for a change in trajectory of an endpoint upon start of the intervention and for a possible shift in pattern of endpoint values soon after intervention, thus allowing for contrasts of both levels and trajectories. After descriptive statistics, mixed effects linear regression, with random intercepts for subject-specific baseline z-score, and random slopes (for inter-subject variation in trajectories over time), will model and compare outcomes over time. Inclusion of quadratic terms for time, and implementation of splines, will avoid unrealistic assumptions of linear changes in outcomes^(25, 26). Baseline covariates and auxiliary variables that predict dropout will be included to adjust for any residual imbalance and to meet the model assumption of dropout at random. Multiple imputations will be used for any missing covariates⁽²⁷⁾.

Primary comparisons will assume complete treatment adherence. Using the methods of Nagelkerke⁽²⁸⁾ and Small⁽²⁹⁾, we will estimate the effect of the intervention among those subjects who adhered to treatment. Robust confirmatory analysis will use generalized estimating equations weighted to adjust for dropout⁽³⁰⁾.

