Key contrasts will compare the level of each endpoint before and after treatment by comparing differences of model-based expected values at the end of treatment and expected values at baseline; expected values arise from implementation of mixed effects models. This approach permits adjustment for relevant changes in patient characteristics over time (e.g. changes in growth and pubertal status) and for any baseline factors predicting dropout. Alternative contrasts will compare slopes of endpoints over time prior to the intervention against the slopes after treatment initiation. Pre-intervention measures will improve statistical power.

Sensitivity analyses will examine the potential impact of informative dropout⁽³¹⁾, although this source of bias will be minimized through subject retention and follow-up after dropout⁽³²⁾. Supplementing models will be complete descriptive reports, including graphical displays of cholesterol and BMI-Z trajectories for each subject.

Potential Problems/Feasibility: Dosing of levothyroxine treatment tends to be weight-based and is not an exact science. The starting daily dose of 0.5-1 mcg/kg/day is less than

full replacement doses since TSH will be in the 5-10 mUI/mL range and we wish to avoid “over-supplementing” and suppressing TSH. TSH will be rechecked 6 weeks after levothyroxine initiation to confirm TSH is in the desired range. After 6 weeks some subjects may not have “optimal” TSH levels and dose adjustments will be required. We expect that by 3 months following levothyroxine initiation, all subjects will have TSH in the desired range, allowing an additional 3 months for the effect of intervention to be realized; in fact, the immediate treatment group will be followed for 12 months, over which time effects upon body composition and CMR factors should be apparent. This study might find that the relationship between subclinical hypothyroidism and CMR factors is pure association, an important finding as the medical community looks for evidence upon which to base management of “mild” TSH elevations in DS. In fact, this finding could avert unnecessary treatment of subclinical hypothyroidism in adolescents with DS.

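### The efficacy models adjust for growth and pubertal change without limiting those terms to values from before the month 6 randomisation, so the month 6-12 levothyroxine-placebo contrast may not estimate the full effect, most directly for HT-Z, WT-Z and BMI-Z

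*Combined protocol and SAP*

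**What the plan says.** Section 6.1.2 sets out the main comparisons: "Key contrasts will compare the level of each endpoint before and after treatment". The expected values behind them come from mixed models that are to "adjust for any relevant changes in patient characteristics over time (such as changes in growth and pubertal status", and for baseline factors that predict dropout. Section 6.1.1 describes the same adjustment as an option: "This approach permits adjustment for relevant changes in patient characteristics over time". Neither section says what growth means, which endpoints receive which terms, or that the terms stop at month 6.

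Section 6.1.1 uses the mixed model "to estimate in a single model both longitudinal (within subject) and cross-sectional (across subject) effects of the intervention". On the between-arm part it adds: "Cross-sectional comparisons will be possible for the second 6-month period of observation". That is the window in which one arm takes levothyroxine and the other placebo. Randomisation follows the month 6 visit (Section 3.1).

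At months 12 and 18, Section 3.1.3 repeats "anthropometric measurements, whole body DXA scan, blood pressure, pubertal assessment and questionnaire assessments". The synopsis lists "Anthropometry (HT-Z, WT-Z, BMI-Z" among the efficacy evaluations. BMI-Z is in the synopsis primary objective and is a secondary hypothesis (a decrease) in Section 2.2. The primary endpoint in Section 2.1 is non-HDL-C.

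**The concern.** Height, weight and Tanner stage at months 12 and 18 are observed after randomisation. If treatment moves one of them, conditioning on it takes out of the treatment contrast whatever passes through it. What remains is not the effect of being assigned levothyroxine rather than placebo.

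The protocol gives some reason to think growth could move. It hypothesises a fall in BMI-Z (Section 2.2). It also cites improved growth velocity after one year of treatment in short children, and better growth and weight gain at 24 months in neonates with Down syndrome (Sections 1.3.2.3 and 1.5). Neither study shows an effect within 6 months at ages 8-20.

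At stake is the only concurrent randomised comparison of drug with placebo. For HT-Z, WT-Z and BMI-Z the covariate would be a component of the outcome itself. Because growth is undefined, the BMI-Z result could depend on a choice made after the data are seen.

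**Working it through.** The plan gives no figure for the effect of this adjustment, so there is nothing to reproduce. The power table in Section 6.2 is used only for its correlations.

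**1. Does the adjustment reach the randomised contrast?** Section 6.1.2 attaches it to the before/after expected values. Section 6.1.1 says both kinds of effect come from a single model. No section plans an analysis that leaves these terms out. The reach is therefore a fair inference from the two sections together, not an express statement.

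**2. General size.** Let τ be the full effect, a the treatment effect on the covariate, and b the covariate's effect on the endpoint, all in SD units. The adjusted effect is τ − a·b. The values of a and b are assumed.

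- a = 0: the adjusted effect is τ, so 100% is kept.
- τ = −0.70, a = −0.5, b = 0.3: −0.70 + 0.15 = −0.55, or 79%.
- τ = −0.70, a = −0.8, b = 0.5: −0.70 + 0.40 = −0.30, or 43%.
- If a·b has the opposite sign to τ, the estimate is inflated.

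**3. BMI-Z.** Assumed inputs: BMI effect −3.3%; height effect 0 to +0.6%; correlation r of height and weight changes 0.2-0.6; SD of log height change (s_H) 0.6-1.0%; SD of log weight change (s_W) 3-6%. Since log BMI = log weight − 2 × log height (plus a constant for units), the log BMI effect is ln(0.967) = −0.0336.

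*Height change entered.* The slope of log BMI change on log height change is r·s_W/s_H − 2.

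- Lowest: 0.2 × 3/1.0 − 2 = −1.4. With a height effect of 0.006, the adjusted effect is −0.0336 + 0.0084 = −0.0252, or 75%.
- Highest: 0.6 × 6/0.6 − 2 = 4.0. The adjusted effect is −0.0336 − 0.0240 = −0.0576, or 171%.
- No height effect: 100%.

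*Both changes on the log scale.* Together they determine log BMI change exactly, so 0% is kept.

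Large-sample simulation on the BMI-Z scale (162 settings, month-12 BMI-Z on group, month 0 and month 6 BMI-Z and age) gives:

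| Month 6-12 change entered | Share of BMI-Z effect kept, median (range) |
|---|---|
| Height | 100% (74-168%) |
| Weight | 45% (19-71%) |
| Both, cm and kg | 22% (12-48%) |
| Both, log scale | about 0% (−1 to 1%) |

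Repeat runs with fewer settings gave the same pattern: 75-171% and 85-124% for height, 15-67% and 17-55% for weight, and 9-27% and 8-16% for both in cm and kg. The rounded ranges in the verdict summarise these.

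**4. HT-Z and WT-Z.** Under assumed effects (height +0.3 or +0.8 cm, weight −2 or −3.5%), entering height change leaves −8 to 0% of the HT-Z effect. Entering weight change leaves 15-20% of the WT-Z effect in kg and about 0% on the log scale.

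**5. Precision of the clean contrast.** Take 10 per arm, equal correlation ρ between visits, and month-12 values compared given the month 0 and month 6 values: SE = √{[1 − 2ρ²/(1+ρ)] × 2/10} in SD units.

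- ρ = 0.5: √(0.6667 × 0.2) = 0.37
- ρ = 0.6: √(0.5500 × 0.2) = 0.33
- ρ = 0.8: √(0.2889 × 0.2) = 0.24

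With coefficients estimated from 20 children, simulation at ρ = 0.5 gives 0.39, then 0.41 with sex and age added, and 0.42 with Tanner stage added. The estimates are unbiased (−0.69 to −0.71 for a true −0.70).

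**The case against.** The strongest reply is that the text places the adjustment on the before/after contrasts, where maturation is a real confounder, and that the word relevant lets the analyst leave growth terms out of growth endpoints. Both points stand in part. The adjustment has a sound purpose there and need not be removed. But nothing limits it to those contrasts, and discretion that is not set down in advance does not protect the randomised comparison.

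A reader might infer more than the documents support:

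- **That the primary endpoint is biased.** No link between treatment, growth and non-HDL-C is quantified, and the effect may be zero.
- **That the adjustment always weakens the effect.** Entering height change can inflate it.
- **That pubertal adjustment removes treatment effect.** No section reports that levothyroxine changes puberty.
- **That weight loss on treatment is expected.** Section 9.4.2 lists it as a symptom of over-replacement, but also says the study dose is not expected to cause such symptoms.
- **That covariates will be picked after the data are seen.** The documents do not say when they are chosen, only that the choice is open.

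**Conclusion.** The concern holds in limited form. As written, the single model can carry post-randomisation growth terms into the month 6-12 levothyroxine-placebo contrast. If treatment affects growth, that contrast does not estimate the full effect of assignment, and the error may run in either direction.

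It is most direct for HT-Z, WT-Z and BMI-Z if height or weight change is entered. For BMI-Z the share kept is roughly 75-170% with height change, 15-70% with weight change, 10-50% with both in cm and kg, and about 0% with both on the log scale. All of these rest on assumed growth effects, SDs and correlations. If treatment leaves height unchanged, height adjustment does nothing to the estimate. The plan should be amended, with medium confidence in the practical impact.

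**What to change.** In Section 6.1.2, with Section 6.1.1 reconciled so that both use the same strength of wording, state that:

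1. The month 6-12 levothyroxine-minus-placebo contrast is reported from a model whose covariates were all measured at or before month 6: month 0 and month 6 endpoint values, sex, age and, if wanted, month-6 Tanner stage.
2. Post-randomisation height or weight change is not a covariate for HT-Z, WT-Z or BMI-Z.
3. Time-varying adjustment for growth and puberty, with growth defined, is kept for before/after contrasts on other endpoints or as a labelled sensitivity analysis.

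The cost is a few sentences and one extra model fit. The added contrast is imprecise (SE about 0.37-0.42 SD at correlation 0.5 with 10 per arm) and should be reported as such. The planned before/after contrasts remain, and no study procedure changes.

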6.1.3 Safety Analysis

To monitor for safety, data will be made available to investigators every 3 months. Since the PI will not be blinded to treatment arm and will be making dose adjustments, TSH data will be available to the PI as soon as it is available.

6.2 Sample Size and Power

Target sample size is 20, but 29 subjects will be enrolled to allow for dropout. Assuming that the dependent variables are continuous, the power calculations using nonparametric tests that would be suitable for both continuous and ordered data are listed below:

Correlation over time	Effect size of interaction (SD)	Power
0.5	0.7	0.84
0.6	0.6	0.71
0.8	0.4	0.82

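### The powers in section 6.2 (0.84/0.71/0.82) do not follow from their printed inputs at face value, and the table does not define its contrast, SD, test, alpha or sidedness

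*Combined protocol and SAP*

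**What the plan says.** Section 6.2 sets a target of 20, with 29 enrolled to allow for dropout. It says that "the power calculations using nonparametric tests that would be suitable for both continuous and ordered data are listed below" and gives three rows:

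| Row | Correlation over time | Interaction effect (SD) | Power |
|---|---|---|---|
| 1 | 0.5 | 0.7 | 0.84 |
| 2 | 0.6 | 0.6 | 0.71 |
| 3 | 0.8 | 0.4 | 0.82 |

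The analysis is described elsewhere. In section 6.1.1, "Estimates will be based on a standard mixed effects piecewise longitudinal data model", with random intercepts and slopes for subjects. The same section adds "Inclusion of quadratic terms for time, and implementation of splines". Section 6.1.2 states the target of inference: "Key contrasts will compare the level of each endpoint before and after treatment", with slopes before and after treatment as an alternative. Section 6.1.1 also remarks that "Pre-intervention measures will improve statistical power". Section 4.3.1 randomises two groups of 10.

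**The concern.** In the table the effect shrinks as the correlation rises. For a change within subjects these two movements nearly cancel, and what is left should lower the power slightly from row to row. The printed power instead drops sharply and then recovers. That suggests the rows do not share one calculation, or that the printed inputs are not the ones used.

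The second difficulty does not depend on the first. A reader cannot tell whether the powers refer to an uncontrolled change in all 20 subjects or to the randomised comparison of 10 with 10. These can differ greatly.

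The table is the only justification of the sample size. Section 6.1.1 also anticipates that a finding of no causal effect would be used: "this finding could avert unnecessary treatment of subclinical hypothyroidism". Reading a null result that way requires knowing what effect 20 completers could detect, and for which contrast.

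**Working it through.** **Inputs.** Correlations, effects, powers and n = 20 are from section 6.2; 10 per group is from section 4.3.1. The documents give no alpha, sidedness, SD scale or correlation structure. I assume two-sided 0.05, outcome SD 1 and compound symmetry.

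**1. Reproducing the table at face value.** The SD of a within-subject change is sqrt(2(1 − ρ)). The standardised change is d = effect / SD of change, and the paired t noncentrality is d × sqrt(20), with 19 df and critical value 2.093. The signed-rank powers are simulated (300,000 runs, exact critical value 52).

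| Row | SD of change | d | Noncentrality | Paired t | Signed-rank | Printed |
|---|---|---|---|---|---|---|
| 1 | sqrt(1.0) = 1.000 | 0.7/1.000 = 0.700 | 3.13 | 0.84 | 0.83 | 0.84 |
| 2 | sqrt(0.8) = 0.894 | 0.6/0.894 = 0.671 | 3.00 | 0.81 | 0.79 | 0.71 |
| 3 | sqrt(0.4) = 0.632 | 0.4/0.632 = 0.632 | 2.83 | 0.77 | 0.74 | 0.82 |

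Row 1 is reproduced by the paired t test. Row 2 is printed about 0.10 too low and row 3 about 0.05 too high. To give the printed powers, the paired t test would need about 19.8, 16.1 and 22.7 subjects.

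**2. Can rounding explain it?** The inputs carry one decimal. Take a one-group signed-rank test on 20 subjects with these unrounded inputs:

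- ρ = 0.50, effect 0.71: d = 0.71/1.000 = 0.710, power about 0.84
- ρ = 0.58, effect 0.56: d = 0.56/0.917 = 0.611, power about 0.71
- ρ = 0.81, effect 0.43: d = 0.43/0.616 = 0.698, power about 0.82

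All of these print as the tabled inputs, so one common nonparametric test can produce the table. The fit for row 2 is narrow. It needs an effect of 0.55 to 0.58 with a correlation of 0.55 to 0.595, about 2.6% of the values that would round to 0.6 and 0.6. At a correlation of exactly 0.6 it needs an effect of 0.540 to 0.546, which would print as 0.5.

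**3. How firm is the row order?** For rows 2 and 3 to have equal power, the contrast variance at correlation 0.8 must be (0.4/0.6)² = 0.444 of that at 0.6. Under compound symmetry the ratio is (1 − 0.8)/(1 − 0.6) = 0.50, so row 3 must be lower. Under AR(1) the smallest ratio is 0.45, almost a tie. With faster correlation decay it falls below 0.444 (0.427 in one case tried), and the order can reverse. Random slopes can also reverse it.

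**4. Which contrast?** Two simple readings match row 1.

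- One-group before-after change, n = 20: step 1.
- Interaction defined as half the difference-in-differences, 10 v 10. The noncentrality is 2d × sqrt(10/2) = 3.13/3.00/2.83 with 18 df. Power is 0.84/0.81/0.76 by t test and 0.80/0.77/0.72 by Mann-Whitney.

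If the tabled effect is instead the full randomised difference in change in raw SD (an assumption), the noncentrality is d × sqrt(10/2) = 1.57/1.50/1.41. Two-visit power is then 0.32/0.30/0.27 by t test and 0.28/0.26/0.24 by Mann-Whitney.

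**The case against.** The strongest reply is that no arithmetic error is proven. One signed-rank test at n = 20 gives all three powers with inputs that round to the printed ones, and that is the class of test section 6.2 names. The planned model has random slopes, which can change the row order. Both points stand. Rounding is a tight fit for row 2, but it is not excluded.

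The table is also not silent. It names an interaction, SD units and a nonparametric class, and sections 3.1 and 6.1.2 make each child's before-after change central, which agrees with the reading that matches row 1. That stands too. What is missing is which interaction, which SD, which test, alpha and sidedness.

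Third, section 1.1 calls the study preliminary, and powering with a simpler test than the analysis model is not in itself a mistake. I agree. But a reader still cannot recover the printed powers from the printed inputs or connect them to the planned analysis.

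A reader might infer that 0.71 is a slip for 0.81. That would bring row 2 into line with the paired t test but leave row 3 at 0.77 against 0.82. A reader might also infer that the trial's true power is about 0.3. The documents do not support that. The figure assumes a raw-SD effect, two visits and two-sided 0.05, whereas the planned model uses four main visits and its power depends on inputs the plan does not give.

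**Conclusion.** The concern holds as a failure of reproducibility and specification; it does not establish that a particular row is wrong. Taken at face value, rows 2 and 3 miss by about 0.10 and 0.05 under a paired t test (0.08 each under signed-rank), and their order is reversed. This rests on outcome SD 1, compound symmetry and an assumed two-sided 0.05. Rounding, faster correlation decay or random slopes could account for it, and the documents cannot say which.

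Independently of the arithmetic, the powers are not tied to the randomised contrast or to the mixed piecewise model. The choice of contrast matters: the same row 1 inputs give 0.84 for a one-group change and about 0.32 for a two-visit randomised difference in change, under the assumptions in step 4. Because the table alone supports the sample size, it should be corrected.

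**What to change.** Recompute section 6.2 on one stated basis, print the inputs with enough decimals, and make each row agree with them. State the test, the contrast, the SD scale (raw, change or residual), alpha, sidedness and n. For the randomised 10 v 10 treatment contrast of the planned mixed model, give the power or the effect detectable at 80% power, with the assumptions used. If a one-group before-after power is kept, label it as uncontrolled. The figures shown here are illustrations and should not be copied in as replacements.

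The cost is a recalculation and rewording of one section. Patients, visits and procedures stay as they are, and no patients should be added on this account. The downside is that the stated power may become less favourable.
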